Consecutive patients who underwent colocolic or colorectal anastomosis for neoplasia, diverticulitis, mesenteric ischemia, iatrogenic or traumatic perforation, or inflammatory bowel disease will be included. Patients younger than 18 years of age, who have a recurrent colorectal cancer, beared peritoneal carcinomatosis or unresectable metastatic disease at time of bowel resection and anastomosis, or who could not provide consent to participate according to individual institution's rules will be excluded. Moreover, patients who were lost to follow-up less than six weeks after surgery and who have not noted a successful ostomy reversal will be excluded - in these cases, it cannot be surely assessed whether AI occurred or not.

Data Collection

Each center will assemble their data either prospectively or retrospectively from a dedicated clinical database. Each center must provide data from at least 500 patients over not more than 10 years to be included, this in order to ensure data consistency and centre proficiency as monitored by adequate case load.

A standardized data collection form will be given by the sponsor. The data will be registered in a standardized and deidentified form which ensures data completion and anonymity. A study-specific identifier will be produced upon completion of data entrance of each patient. The study database will not have any identifiable patient data. Contributing centers will maintain a log file in which the study-specific patient numbers can be followed to center-specific patient-numbers, in case of a necessity.

Primary Endpoint Definition

AI (Anastomotic insufficiency/leakage) is defined according to Gessler et al. [6] and Rahbari et al. [9] as any clinical signs of leakage, confirmed by radiological examination, endoscopy, clinical examination of the anastomosis, or upon reoperation.

Secondary Endpoint Definitions

AI will be **graded** retrospectively conferring to the system suggested by Rahbari et al. [9] Anastomosis **takedown** is defined as an interruption of the continuity of the bowel and the formation of a stoma, which will be captured in the database. In cases of AI, **death** will be recorded within 90 days from index surgery. In cases of AI, **time to diagnosis of a leakage** will be calculated as days between the index operation and diagnosis of the leakage by imaging with extraluminal contrast, endoscopy, reoperation, or when fecal containing fluid is objectified in a drainage.

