Tertiary Endpoint Definitions

To investigate a potential relationship between AI and oncologic outcomes in a further dedicated study along a 5-year follow-up:

- Disease-free survival (months)
- Overall survival (months)
- Adjuvant/additive immunochemotherapy (yes/no)
- Adjuvant/additive radiotherapy (yes/no)
- Additive curative surgery (no/yes: liver; lung; locoragional relapse)

Features and Their Definitions

All features are measured preoperatively within 30 days of index surgery. The following data will be collected.

For colon-to-colon anastomosis:

- Active smoking (yes/no, pack/years) [10, 11]
- Alcohol abuse (>2 alcoholic beverages per day) [11]
- Height / Weight / BMI [5]
- Preoperative leukocyte count (in $\times 10^3$ per mm^3) [7]
- Preoperative steroid use (mg) [3, 4]
- Preoperative non steroidal inflammatory drug use (NSAID)
- Neoadjuvant chemotherapy (yes/no)
- Charlson Comorbidity Index (CCI) [12]
- American Society of Anesthesiologists (ASA) Score [13-15]
- Renal function (CKD Stages G1 (normal) to G5) [7]
- Nutritional status (NRS ≥ 3) [16]
- Hypoalbuminemia (<3.5 g/dL) [17-19]
- Hemoglobin level (in g/dL) [20, 21]
- Prior abdominal surgery (any) [22]
- Liver metastasis at time of anastomosis (any) [22]
- Age (yrs.)
- Albumin and Prealbumin
- Perioperative blood transfusion
- Psychosocial diseases
- Gender (M/F) [12, 15, 18, 22, 23]
- Anastomotic configuration (stapler anastomosis, stapled and suture closure of stapler enterotomy, hand-sewn; end-to-end; side-to-end; pouch to end)
- Emergency surgery (yes/no)
- Approach: Laparoscopic, transanal, robotic, open
- Extended resection
- Conversion to laparoscopic/open surgery (yes/no)
- Left hemicolectomy / right hemicolectomy / extended left hemicolectomy / extended right hemicolectomy / ileocaecal resection / transverse colectomy / sigmoid resection
- Perforation (yes/no; when yes within 5cm from tumor (yes/no))
- Protective ostomy (yes/no)
- Intra- and postoperative complications

- Date of discharge and discharge status
- Postoperative leucocyte count and CRP level up to 10 days postoperative
- Oncologic resection (yes/no; requires at least 12 LN and integrity of mesocolic/mesorectal planes)
- Indication (Neoplasia, IBD, perforation, diverticulitis, mesenterial ischemia)
- In case of colon cancer, preoperative carcinoembryonic antigen (CEA, ng/ml) and pathological TNM staging according to TNM 8th edition (T, N, M, L, V, Pn, grading (high, low), resection status (R0, R1, R2)

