- In case of colon cancer length of follow-up, disease-free and overall survival

For colo-rectal anastomosis:

- Preoperative tumor stage (MRI): Local (cT) [24-26]
- Preoperative tumor stage (MRI): Nodal (cN) [24, 26]
- Preoperative circumferential and distal margins (MRI)
- Preoperative endovascular margin (MRI)
- Preoperative tumor stage (CT thorax abdomen): Metastasis (cM) [24, 26]
- Neoadjuvant radiotherapy (yes/no) [26-28]
- Neoadjuvant chemotherapy (yes/no)
- Active smoking (yes/no, pack/years) [11, 29]
- Alcohol abuse (>2 alcoholic beverages per day) [11, 30]
- Height / Weight / BMI [31]
- Preoperative leukocyte count (in $\times 10^3$ per mm^3) [7]
- Preoperative steroid use (mg) [3, 4, 32]
- Preoperative non steroidal inflammatory drug use (NSAID)
- Charlson Comorbidity Index (CCI) [12]
- American Society of Anesthesiologists (ASA) Score [13, 14, 32]
- Renal function (CKD Stages G1 (normal) to G5) [7, 33]
- Nutritional status (NRS ≥ 3) [16, 34]
- Hypoalbuminemia (<3.5 g/dL) [17-19]
- Hemoglobin level (in g/dL) [20, 21, 35]
- Prior abdominal surgery (any) [22]
- Age (yrs.)
- Albumin/Prealbumin
- Perioperative blood transfusion
- Psychosocial diseases
- Liver metastasis at time of anastomosis (any) [22]
- Gender (M/F) [12, 18, 22, 26, 27, 34, 36, 37]

- Emergency surgery (yes/no)
- Approach: Laparoscopic, robotic, open
- Extended resection
- Conversion to open surgery (yes/no)
- Anastomotic configuration (stapler anastomosis, hand-sewn; end-to-end; side-to-end; pouch to end)
- Number of stapler cartridges used
- Intra- and postoperative complications
- Anal verge distance (cm) from the tumor lower edge [12, 22, 24-27, 32, 38]
- Anal verge distance (cm) from the anastomosis [12, 22, 24-27, 32, 38]
- Circumferential margin (mm)
- Protective ostomy (yes/no)
- Type of anastomotic testing
- Postoperative leucocyte count and CRP level up to 10 days postoperative
- Date of discharge and discharge status
- Indication (Neoplasia, IBD, perforation, diverticulitis, mesenterial ischemia)
- In case of rectal cancer, preoperative carcinoembryonic antigen (CEA, ng/ml) and pathological TNM staging according to TNM 8th edition (T, N, M, L, V, Pn, grading (high, low), resection status (R0, R1, R2)
- In case of rectal cancer length of follow-up, disease-free and overall survival

Sample Size

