For this study, based on our expertise and on the rules of thumb mentioned above, we approximated that a minimum of 250 patients with AI are needed to identify generalizable features. With an incidence of AI of 5% for colon anastomosis and 8% for colorectal anastomosis, that means that a minimum of 5000 and 3125 patients are required for training for each population (colocolic and colo-rectal anastomosis, respectively). For satisfactory evaluation of calibration at external validation, we estimate that another 2000 and 1250 patients per cohort (thus, approximately 100 with AI per cohort) will be required. Thus, in total, we estimate that **7000 (colocolic anastomosis) and 4375 (colorectal anastomosis) patients** are necessary to reach at a satisfying model. More data will likely lead to greater performance and better calibration.

Predictive Modeling

A KNN imputer will be co-trained to impute any missing data that may occur in future application of the model. If there is missing data in the training set, it will be imputed using said KNN imputer. [39] Features or patients with a missingness greater than 25% will be excluded. Data will be standardized and one-hot-encoded. In case of major class imbalance – which is expected for the abovementioned endpoint – random upsampling or synthetic minority oversampling (SMOTE) will be applied to the training set. [40, 41] All features will at first be given to the model for training. If needed, we will employ recursive feature elimination (RFE) to choose input features on the training data. [42]

We will trial the following algorithms for binary classification: Generalized linear model (GLM), generalized additive model (GAM), stochastic gradient boosting machine (GBM), naïve Bayes classifier, artificial neural network, support vector machine (SVM), and random forest. Each model will be fully trained and hyperparameter tuned where applicable. The final model will be selected based upon (AUC), sensitivity, and specificity, as well as calibration metrics on the resampled training performance. Training will happen in repeated 5-fold cross-validation with 10 repeats.

The one final model will then be examined on the external validation data only once. Ninety-five percent confidence intervals for external validation metrics will be derived using the bootstrap.

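### The colon-to-colon anastomotic configuration item has no side-to-side or other level, so the geometry part of this PANIC-C predictor will be degraded if the protocol's definition is followed

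*Protocol*

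**What the plan says.** Under Features and Their Definitions, the colon-to-colon list gives the item "Anastomotic configuration (stapler anastomosis, stapled and suture closure of stapler enterotomy, hand-sewn; end-to-end; side-to-end; pouch to end". Three of its entries describe technique and three describe geometry. None is side-to-side, and there is no other category.

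The same list records the type of resection as "Left hemicolectomy / right hemicolectomy / extended left hemicolectomy / extended right hemicolectomy / ileocaecal resection / transverse colectomy / sigmoid resection". Right hemicolectomy, extended right hemicolectomy and ileocaecal resection are therefore within the population that this list serves.

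The colorectal list has a near copy of the item, "Anastomotic configuration (stapler anastomosis, hand-sewn; end-to-end; side-to-end; pouch to end". It lacks the level for sutured closure of a stapler enterotomy and has the same three geometries.

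Under Data Collection, the form itself is left to the sponsor: "A standardized data collection form will be given by the sponsor".

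Under Predictive Modeling, "All features will at first be given to the model for training" and "Data will be standardized and one-hot-encoded". Missing training values are filled by a KNN imputer, and "Features or patients with a missingness greater than 25% will be excluded".

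**The concern.** A categorical predictor should have a level for every patient who can be enrolled. The colon-to-colon item appears to have been adapted from the colorectal one on the technique side only: it gains a level for sutured closure of a stapler enterotomy but keeps the three geometries unchanged. That closure step most naturally accompanies a linear-stapled side-to-side join. The list thus anticipates the technique without offering the geometry that usually goes with it.

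At stake is the meaning of the geometry levels in PANIC-C. If centres place side-to-side joins under different listed geometries, the same indicator describes different operations at different centres, and any association with leakage is blurred. If they leave geometry blank, the imputer supplies a geometry that the patient did not have. The planned web tool would inherit the gap, because a user whose patient has a side-to-side join would find no correct entry.

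**Working it through.** **1. The levels side by side (Protocol, Features and Their Definitions).**

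| | Colon-to-colon list | Colorectal list |
|---|---|---|
| Technique | stapler; stapled with sutured enterotomy; hand-sewn | stapler; hand-sewn |
| Geometry | end-to-end; side-to-end; pouch to end | end-to-end; side-to-end; pouch to end |
| Side-to-side | absent | absent |
| Other | absent | absent |
| Right-sided or ileocaecal resections listed | yes | no |

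Side-to-side is not mentioned anywhere in the protocol. The last row is why the consequence is argued for the colon-to-colon list only.

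**2. What the modelling rules do with a side-to-side join (Protocol, Predictive Modeling).**
- Recorded under a listed geometry: one-hot encoding switches on the wrong indicator.
- Left blank: KNN imputation borrows from similar patients. No training record carries side-to-side, so the imputed value can only come from the three listed geometries. Such blanks would not be random; they would cluster in right-sided and ileocaecal resections.
- Left blank in more than 25% of patients: the feature is excluded.

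**3. The plan's own figure (Protocol, Sample Size).** Patients = leakage cases / incidence.
- Training: 250 / 0.05 = 5000.
- External validation: 100 / 0.05 = 2000.
- Total for PANIC-C: 5000 + 2000 = 7000, as stated.

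This total is used below only as a denominator.

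**4. How many patients could be affected.** Let r be the right-sided or ileocaecal share of PANIC-C and s the side-to-side share among those patients. The protocol gives neither, so both are assumptions. Share without a correct geometry level = r × s; number = 7000 × r × s.

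| r | s | r × s | Patients of 7000 | Above 25%? |
|---|---|---|---|---|
| 0.30 | 0.25 | 0.075 | 525 | no |
| 0.30 | 0.90 | 0.27 | 1890 | yes |
| 0.40 | 0.75 | 0.30 | 2100 | yes |
| 0.50 | 0.50 | 0.25 | 1750 | no (exactly 25%) |
| 0.60 | 0.90 | 0.54 | 3780 | yes |

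The last column matters only if geometry is a separate field and every such patient is left blank. The scenarios fall on both sides of the limit, so the documents do not settle whether the exclusion rule would apply.

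**The case against.** The strongest reply is that the protocol list is not the form. The sponsor supplies a standardized form that is not shown, and several neighbouring items, such as extended resection or type of anastomotic testing, have no levels at all. Answer options are normally settled on the form. This stands as a limit: a reader might infer that side-to-side joins cannot be recorded in this study, and the protocol does not support that. The omission is shown only for the protocol's own definition. It is still more than missing detail, because this item does state its levels and the stated set is incomplete.

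Second, the protocol does not say that side-to-side joins are common after the listed resections, or that sutured enterotomy closure implies one. Both are general surgical knowledge. That is enough to ask for the level but not to size the effect.

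Third, a reader might infer that the model loses the predictor altogether. It does not. Technique stays recordable, and the sutured-enterotomy level probably carries some of the missing information. Type of resection is a separate feature. If the item is one field, an entry for technique already fills it and the 25% rule is not triggered by that patient. The aim is prediction, not estimating the effect of configuration, and no loss of AUC or calibration is shown.

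Fourth, the punctuation already largely separates technique from geometry: commas divide the techniques, and a semicolon precedes the geometries. This mostly stands, so mixing the two is not a fault of weight in itself. Semicolons also divide the geometries from each other, however, so stating two fields removes doubt at little cost.

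Fifth, a reader might extend the point to PANIC-R, since the colorectal item has the same gap. The omission there is a fact, but the right-sided and ileocaecal resections are not in that list and the protocol shows no consequence.

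**Conclusion.** The point holds in a limited form. The level set of the colon-to-colon configuration item is incomplete for the operations that the same list covers. Followed as written, it gives side-to-side joins a false geometry, either by hand or by imputation, and so degrades the geometry part of this predictor in PANIC-C.

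The size is not determined by the documents. Under the assumed shares it runs from 525 to 3780 of 7000 patients. The conclusion rests on two assumptions: that side-to-side joins occur in appreciable numbers after the listed resections, and that the form has the same levels as the protocol. If the form already has the level, what remains is to align the protocol text with it.

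The documents do not support saying that the predictor will be dropped under the 25% rule, that PANIC-R is harmed, or that the sample size or endpoint is affected.

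**What to change.** - In the colon-to-colon item, add side-to-side and other to the geometry levels.
- State technique (stapled; stapled with sutured enterotomy; hand-sewn) and geometry (end-to-end; side-to-end; side-to-side; pouch to end; other) as two fields, each one-hot encoded separately.
- Check the sponsor's data collection form against these levels and make the two agree. If the form already has them, only the protocol text changes.
- Using the same geometry levels in the colorectal list is optional, for consistency.

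The cost is small before data entry: one or two levels, and one field if technique and geometry are not already separate on the form. Centres supplying retrospective data may not have geometry coded separately. They would have to look it up or mark it as unknown, which is better than entering a geometry known to be wrong.

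### PANIC-R applies one 25% missingness limit and KNN imputation to tumour-only fields, although patients without a tumour are eligible; the numeric fields are certainly affected, the categorical ones only if left blank

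*Protocol*

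**What the plan says.** **Population.** The section Inclusion and Exclusion Criteria sets eligibility as follows: "Consecutive patients who underwent colocolic or colorectal anastomosis for neoplasia, diverticulitis, mesenteric ischemia, iatrogenic or traumatic perforation, or inflammatory bowel disease will be included". The colorectal feature list also records indication, with the non-neoplastic groups as levels, so PANIC-R expects patients without a tumour.

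**Features.** Seven bullets in the colorectal list describe a tumour and carry no cancer condition:
- "Preoperative tumor stage (MRI): Local (cT") and the corresponding cN and cM items;
- "Preoperative circumferential and distal margins (MRI") and the MRI endovascular margin;
- "Anal verge distance (cm) from the tumor lower edge";
- the circumferential margin in mm.

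Only the last two bullets (CEA with pathological staging, and oncologic follow-up) are made conditional on rectal cancer.

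**Handling of gaps.** Predictive Modeling states: "Features or patients with a missingness greater than 25% will be excluded". Gaps in the training set are filled by a KNN imputer, which is co-trained so that it can also fill gaps when the model is used later. Data are standardized and one-hot-encoded, and every listed feature is offered to the model at the outset. Expected Results promises a web tool for each model.

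**Data form.** Data Collection says: "The data will be registered in a standardized and deidentified form which ensures data completion and anonymity". The form itself is not shown.

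**The concern.** A tumour distance in a patient operated on for diverticulitis is not a value that somebody failed to record; it does not exist. The missingness rule makes no such distinction, so a field left empty for this reason meets one of two fates.

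- If total missingness exceeds 25%, the field is removed for tumour patients too, even if it was fully recorded in them. Case mix rather than predictive value then decides whether it stays.
- If not, a value is imputed. Only tumour patients have recorded values, so every donor is a tumour patient, and the model is trained partly on tumour measurements of people without a tumour. If the field stays in the final model, the co-trained imputer could do the same for a benign patient in the web tool.

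The protocol itself fixes both the limit and the imputation method, so this is a stated rule that does not fit the stated population.

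**Working it through.** **Inputs from the protocol (Sample Size).** 250 AI cases for training, about 100 for external validation, 8% incidence for colorectal anastomosis. These reproduce the plan's figures: 250/0.08 = 3125 training patients, 100/0.08 = 1250 validation patients, 4375 in total.

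**Assumptions (not in the protocol).** b = share of PANIC-R patients without a tumour; m = ordinary missingness of a tumour field among tumour patients. The field is left blank in patients without a tumour.

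**Step 1: when the field is dropped.** Missingness = b + (1-b)m. Setting this to 0.25 gives a break-even of b = (0.25 - m)/(1 - m).

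| m | break-even b |
|---|---|
| 0 | 25.0% |
| 5% | 0.20/0.95 = 21.1% |
| 10% | 0.15/0.90 = 16.7% |
| 15% | 0.10/0.85 = 11.8% |

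Above the break-even the field goes for all. At b = 30% and m = 0, the recorded values of 0.70 × 3125 = 2187.5, about 2188 training patients, are discarded.

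**Step 2: when the field is kept and imputed.**
- b = 10%: kept if 0.10 + 0.90m ≤ 0.25, so m ≤ 16.7%. Affected: 0.10 × 3125 = 312.5, about 312 training patients.
- b = 20%: kept if 0.20 + 0.80m ≤ 0.25, so m ≤ 6.25%. Affected: 0.20 × 3125 = 625 training patients and, if the imputer is used there, 0.20 × 1250 = 250 validation patients. If the 8% incidence also holds in patients without a tumour (a further assumption), 0.08 × 625 = 50 of the 250 training AI cases carry imputed tumour values.

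**Step 3: how many fields.** Two fields have stated units (cm, mm). At b = 20% that is 2 × 625 = 1250 imputed values. The MRI margins add to this if they are recorded as numbers. cT, cN and cM add to it only if they are left blank.

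**Step 4: why the numeric fields differ.** A not-applicable level of a categorical field is a recorded value and becomes its own column under one-hot encoding, so neither the limit nor the imputer touches it. A distance or margin has no such level. A not-applicable mark on the form still leaves no number for the model, and the protocol offers only deletion or imputation.

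**The case against.** **The form may already solve this.** Coding of not-applicable entries is usually settled in a data dictionary or SAP, and Data Collection promises a form that secures completeness. This stands for cT, cN and cM. A reader might infer that a not-applicable code would itself be caught by the 25% rule. It would not, because a recorded level is not missing data. Nor does the protocol support counting all eight tumour variables as affected (8 × 625 = 5000 values at b = 20%); that holds only if every one of them is left blank. The numeric fields remain.

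**b may be small.** Sigmoid resection appears in the colon-to-colon list, so some diverticulitis cases may fall into PANIC-C. This does not show that b is small, but nothing in the protocol supports 20% or 30% either. They are illustrations.

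**Harm to the model is not shown.** This is correct. The counts above are patients and values, not changes in AUC or calibration. Indication is a listed feature. In a GLM, an indicator plus a constant fill gives the same fitted values whatever the constant, so KNN filling alongside indication differs mainly through the variability of donor values. Recursive feature elimination and external calibration are further checks. A reader who infers a miscalibrated model goes beyond the documents. Even so, indication prevents neither deletion nor imputation.

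**Dropping a feature that many patients lack is a defensible rule for one model serving all indications.** In part. "Anal verge distance (cm) from the anastomosis" stays in the list and partly replaces tumour height. It does not replace the margins, and the rule would discard a field that may be complete in every patient to whom it applies.

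**Exclusion of benign patients.** A reader might infer that the patient-level limit removes patients for having no tumour. That depends on how composite items are split and which items count as features. The protocol does not settle this, so the conclusion is not drawn here.

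**Conclusion.** The point holds in limited form. The PANIC-R population includes patients in whom tumour fields cannot exist, and the missingness rule has no provision for them. This is certain for tumour distance and circumferential margin, likely to extend to the MRI margins if they are numeric, and conditional on blank entries for cT, cN and cM.

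Which branch applies depends on b and m, both unknown. The field is lost to all patients above a break-even b that falls from 25.0% at m = 0 to 16.7% at m = 10%. Below it, roughly 312 (b = 10%) to 625 (b = 20%) of 3125 training patients receive tumour values that they cannot have. Neither branch is sound if b is material, and the effect is small if b is small. The consequence for predictive performance is unquantified and softened by indication. The sample size is unaffected. The rule should be corrected before modelling starts, since the external validation data are to be used only once; it is not a fatal flaw.

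**What to change.** Add to Predictive Modeling, in substance:

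> Tumour-specific fields in patients without a tumour are coded as not applicable: a category of its own for categorical fields; for numeric fields, a constant fixed in advance together with a tumour-present indicator. Not-applicable entries are not imputed and do not count toward the patient-level 25% limit. For these fields, the 25% feature limit and KNN imputation apply only among patients with a tumour, in training, external validation and the web tool.

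The indicator can be derived from indication where possible. Apply the same rule to the fields that either list makes conditional on colon or rectal cancer, among the patients to whom they apply, if they are used as predictors.

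With this change a tumour field's missingness is m among tumour patients, not b + (1-b)m, so case mix no longer decides its fate.

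Cost: a few sentences, a not-applicable code and at most one yes/no item on the data form; no added patients or examinations. The downside is that the constant enters distance-based methods such as KNN and SVM, so it must be fixed before modelling.
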